14.7 Risk Assessment and Reporting SOP

All researchers and clinicians that have direct contact (by telephone or email) with recruits or participants will be familiar and trained how to use this SOP and will sign the delegation log to say that this has been done. The purpose of the SOP is to script the contact between researcher and participant so that the risk is assessed.

Pls/supervisors/clinicians (e.g., local psychiatrists or clinical psychologists) will also familiarise themselves with this SOP and provide researchers with their contact details in case the researcher needs advice. When clinical academic staff are away on leave they should ensure appropriate cover is arranged to support researcher with advice on for any risk issues that might arise in their absence. The clinician is available to support and guide the researcher in responding to risk and where requested in communicating and providing guidance to the participant.

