14.8 Telephone contact

When conducting telephone interviews or providing on-demand telephone support in which risk may be disclosed, the interviewer should establish the telephone number and location of the participant at the start of the call, and clarify the boundaries of confidentiality:

'Hi, is that (name) this is X from the Nurture-U Bounce-Back trial, is now a convenient time to talk?' [or in response to answering a call direct from a participant – at which point we would ask for name and email, so we can identify them]

If yes 'This call is confidential and the only reason I would break that is if I thought you were at risk to yourself or others and it was in your best interests.

We just wanted to give you a call after your message to us in the email you sent / I would like to clarify what you are telling me now on the phone.

Can I just check where you are at the moment? [obtain details of location/address]

"I see that you've said / you mentioned that....... (examples: if thoughts of death /"what is the point?" / "it might be better if I did not wake up",

"Has this gone as far as thinking about harming yourself or killing yourself?" If yes, or if already stated:

'These are common thoughts and can vary a lot in their severity and it's important to make sure you are receiving the right kind of support. So I would now like to ask you some more questions that will explore these feelings in a little more depth."

INTENTION

Have you had any intention to hurt or kill yourself? YES OR NO

PLANS

1 Do you know how you would kill yourself?

Yes / No

If yes – ask for and record details

2 Have you made any actual plans to end your life?

Yes / No

If yes – ask for and record details

ACTIONS

3. Have you made any actual preparations to kill yourself? Yes / No

If yes - ask for and record details

4. Have you ever attempted suicide in the past?

Yes / No

If yes - ask for and record details

6. **PREVENTION** Is there anything stopping you killing or harming yourself at the moment? Yes / No

If ves – ask for and record details

7. Do you feel that there is any immediate danger that you will harm or kill yourself?

Yes / No

Ask for and record Details:

If yes to any of questions 1-4

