- [if yes to 4 only, or yes to 1 only] I can see that things have been very difficult for you, but it seems to me these thoughts about death are not ones you would act on would this be how you see things? (if they say yes) I would advise you to make an appointment to see your GP to talk about these feelings.
- [if any of 1-3] Would you like us to write a letter to your GP letting them know how you are feeling? If yes, please can you give us your permission to do so (and provide their contact details)
- [all] I can also email you a list of website and helplines for people that have expertise at helping in just this kind of situation, would that be helpful?

If yes to 2 and 3 or to 6, request clinical input if not a clinician and say the following

- I am very concerned about your safety at this moment....
- I am not a clinician, but I would like you to talk to one right now. With your permission I am going to call the site clinician/your GP to let them know how you are feeling and to arrange for you to receive immediate help/a call back. Can you provide their contact details?

In addition, If yes to question 6 [immediate risk]

• I think its best that you get emergency support at this time. I am going to call your GP/the emergency services and send them to your location.

Keep the participant on the phone while you call the clinician from another number or email.

If immediate risk is disclosed the interviewer should not hang up if at all possible.

In case contact is lost, the participant should be informed that the interviewer / supervisor will call them back straight away but that if they are unable to make contact the participant's G.P. or the emergency services will be informed. Good practice is to call /use a phone line for participants that (a) is mobile so that researcher can contact clinical supervisor if physically proximal (b) have a second line to contact clinical supervisor (e.g., by text) whilst maintaining conversation with participant.

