14.10 Risk register

All risk alerts whether via email or telephone contact will be logged on a risk register with any action taken, by whom and when (see below). Site researchers will follow up on risk alerts within 1 working day using the risk assessment and reporting SOP including responding to participant and registering the action taken. This will need to be logged at each local site and shared centrally with the lead site (Exeter) in an anonymised format.

14.11 Action to take after responding to immediate risk:

- 1. Document action taken on the risk log and a risk report form (see below).
- 2. Send letter electronically or by post to GP documenting information gathered and action taken.
- 3. Seek / offer supervision around support and debriefing as appropriate.

Figure 3

Risk Report Form

Participant Trial Number

Supervisor:	Signed:	Date://_	
Researcher / assessor / supporting PWP: _	Signo	ed: Date:	//
Date action taken://			
Additional notes / actions taken:			
Date reported://			
Immediate risk:			
Prior attempts:			
Prevention:			
Actions:			
Plans:			
Suicide risk information: [note answers to Intention:	all questions above re	e yes/no answers and (details]

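### Protocol 14.8: both urgent telephone rules cite item 6, a protective question; the immediate-danger question is item 7 and no numbered rule cites it

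*Protocol*

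**What the plan says.** Protocol section 14.7 gives the aim of the procedure: "The purpose of the SOP is to script the contact between researcher and participant so that the risk is assessed". Section 14.8 then lists the questions for a telephone call. After an un-numbered question on intention, the printed numbers run 1, 2, 3, 4, 6, 7; there is no item 5. The last two items are:

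- "6. PREVENTION Is there anything stopping you killing or harming yourself at the moment"
- "7. Do you feel that there is any immediate danger that you will harm or kill yourself"

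Three levels of response follow:

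- A yes to any of items 1 to 4 leads to advice to see the GP, the offer of a letter to the GP, or a list of helplines, depending on which item.
- Clinical input: "If yes to 2 and 3 or to 6, request clinical input if not a clinician and say the following".
- Emergency support, meaning a call to the GP or the emergency services: "In addition, If yes to question 6 [immediate risk".

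Some steps carry no item number. One is "If immediate risk is disclosed the interviewer should not hang up if at all possible". There is also a procedure for lost contact, and a later section headed "14.11 Action to take after responding to immediate risk" covers documentation, a letter to the GP and supervision.

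**The concern.** Both urgent rules turn on item 6. As printed, a yes to item 6 means that something is stopping the participant from self-harm, which is a protective answer. The answer that should lead to urgent action is a yes to item 7, and no numbered rule refers to it. The rules therefore respond to the wrong question.

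These two rules decide when a clinician is brought into a call and when the GP or emergency services are contacted. The scripted wording for the clinical-input step has the caller's interviewer say that they are not a clinician, so the procedure expects non-clinical staff to rely on it during a crisis call. What is at stake is participant safety, not the trial's estimates.

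**Working it through.** **Items and rules side by side (all from section 14.8)**

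| Printed item | Content | Meaning of yes | Numbered rules that cite it |
|---|---|---|---|
| 1 to 4 | Method known, plans, preparations, past attempt | Raised risk | GP advice, letter and helplines; items 2 and 3 together also trigger clinical input |
| 6 | Prevention | Protective | Clinical input; emergency support |
| 7 | Immediate danger | Immediate risk | None |

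**Evident intent.** The emergency rule labels its own trigger as immediate risk, which fits item 7 and not item 6. The risk report form (Figure 3) has separate fields for prevention and immediate risk, so the two questions are distinct. Number 5 is skipped. Had the numbering been consecutive, prevention would be 5 and immediate danger 6, and both rules would be correct.

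**Counting the effect.** Six yes/no items give 2^6 = 64 answer patterns. Write each item number for a yes to it, and read the words joining 2 and 3 as requiring both.

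- As numbered: clinical input = (2 and 3) or 6; emergency = 6.
- As intended: clinical input = (2 and 3) or 7; emergency = 7.

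*Emergency decision.* The two versions differ whenever items 6 and 7 have different answers: 64 × 1/2 = 32 patterns. In 16 (7 yes, 6 no) the response is missed; in 16 (6 yes, 7 no) it is unneeded.

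*Clinical-input decision.* The versions differ in those same 32 patterns unless 2 and 3 are both yes, which makes the rule fire either way. Both are yes in 1/4 of patterns, so 32 × 3/4 = 24 differ: 12 missed and 12 unneeded.

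*Critical group.* Among the 16 patterns with immediate danger and nothing stopping the caller (7 yes, 6 no), emergency support fires in 0, and clinical input in 16 × 1/4 = 4.

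**Sensitivity to the reading of 2 and 3.** If a yes to either item were enough, clinical-input decisions would differ only where both are no: 32 × 1/4 = 8 patterns. Clinical input would then fire in 16 × 3/4 = 12 of the critical 16. The emergency counts do not change.

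**The case against.** The strongest reply is that trained staff would see what was meant, and that the protocol offers other routes to a clinician.

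- The bracketed label says what the emergency trigger is. Because that rule is introduced as an addition to the clinical-input rule, the label arguably explains the number in both.
- The scripted expression of serious concern would make no sense after a protective answer.
- Section 13.1 lets a researcher with serious concerns consult the designated clinician whatever the item numbers, and section 14.7 makes clinicians available to guide the response.
- Section 14.8 itself has an un-numbered line about calling the clinician while keeping the participant on the phone.
- Pattern counts give every combination equal weight, and any mis-cited yes/no item would produce disagreement in half of them.
- The missing item 5 might reflect a disturbed page layout in the extracted text.

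Much of this stands as mitigation: a caller in danger is not left without any route to help, and the counts say nothing about how often the problem would arise. But the general routes depend on judgement, whereas these rules were written so that staff need not improvise. The clinical-input rule itself carries only the number, and the reader has to borrow the label from the rule after it. The layout point is weak, because 6 and 7 are printed beside their questions and 6 appears in both rules. None of this makes the cross-references correct.

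**Conclusion.** The concern holds. Both urgent rules in section 14.8 cite the protective question, and the immediate-danger question triggers no numbered rule. Taken literally, the emergency decision is wrong in 32 of 64 answer patterns and the clinical-input decision in 24 of 64 (8 of 64 if either of items 2 and 3 suffices). These figures describe the logic of the rules, not the callers; the protocol gives no frequencies. They rest on two assumptions: that item 7 was the intended trigger, which the label and the skipped number support, and that staff follow the numbers rather than the label.

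It is a numbering slip with a recoverable intent and no bearing on endpoints or analysis. Because it sits in an operative safety rule, it should be corrected and not left to training.

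**What to change.** Make one of two changes, not both: renumber the prevention question as 5 and the immediate-danger question as 6, or leave the items as they are and change 6 to 7 in the clinical-input and emergency rules. In either case, put the wording of the triggering question into each rule so that it no longer depends on a number alone. Ask the clinical lead to confirm which answers trigger which action, including whether items 2 and 3 must both be yes, and re-brief the staff who use the procedure.

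The cost is two digits, two short additions of wording and a brief re-briefing.

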14.9 E-mail contact

In the eventuality that participants send emails to researchers or receiving on-demand e-mail support that indicate potential elevated suicide risk (e.g. talking about death, ending it all, seeing no hope, referring to suicide or self-harm, seeing no way out), then further follow-up steps will be taken, including attempts to respond to the participant to clarify the severity of the risk. These emails will provide guidance and signposting information (replicating the information provided on the automated webpage in response to reporting suicidality on the screening/assessment website) and enquire about risk following the questions above (e.g., asking about suicidal ideation, thoughts, plans, preparation, prevention, means).

An email will be sent to participant, acknowledging their potential distress and thoughts of death and self-harm, including the following questions:

Self Risk Q1 Are you currently experiencing any thoughts about suicide?

Self Risk Q2 Do you have any intention to hurt or kill yourself?

Self Risk Q3 Have you made any current plans to end your life or harm yourself?

Self Risk Q4 Do you have the means to harm yourself or end your life?

A template email for initial response is as follows, to be adapted to directly respond to details and concerns raised in specific email from the participant:

"Dear

Thank you for contacting us.

Your email suggested that you might have been having thoughts about harming or killing yourself. These thoughts can vary a lot from person to person. These may have just been brief passing thoughts or reflect a sense of feeling trapped, but without any intention to do anything. These thoughts are relatively common and not that unusual in people who feel stressed.

On the other hand, you may have been thinking about your death a lot, or you may have thought about killing yourself. You may have even have thought about how you might kill yourself or made a plan to end your life. In any of these cases, we strongly urge you to talk to someone about these thoughts, and in particular your GP or family doctor.

It would be useful to know more about the sort of thoughts you are having at the moment. Are they just thoughts about death? Or are you having thoughts about killing or harming yourself? If it is the latter, have you made any actual plans to end your life? Have you made any actual preparations to kill yourself? Is there anything stopping you killing or harming yourself at the moment? I would appreciate you letting me know the answers to these questions, so I can help you as best I can.

If you are having thoughts of ending your life or harming yourself, I advise you to contact your general practitioner or family doctor or mental health professional as soon as possible and tell them how you are feeling. If you don't think you can stay safe, please go to the nearest hospital accident and emergency room or contact one of the suicide hotlines at Befrienders.org or Samaritans.org. If none of these options are available, please contact a family member, a trusted friend, or any other trusted person so that you won't be alone right now.

Throughout the UK, please contact your GP using the normal telephone number for your GP practice. If the surgery is not open, you will either be re-directed automatically to the out-of-hours GP service

or you will be given another number to call. You can also **phone 111 to access the NHS 111 service**, which provides access to local NHS healthcare services in England, and is available 24 hours a day, 365 days a year. Details for out of hours services and support across the UK can be found in the leaflet on national out-of-hours services which has been attached to this email.

If you don't think you can stay safe, please go to the nearest hospital accident and emergency room. If none of these options are available, please contact a family member or a trusted friend, so that you won't be alone right now. If you have already made a plan, as best you can, please try and get rid of the means to harm yourself, whilst keeping yourself safe. It can also be helpful to focus on anything that may stop you from killing or harming yourself at the moment, such as thinking about your faith, loved ones, family and pets. It is important to remember that these feelings and urges do pass, and when individuals feel better, they are glad that they did not act on them. There are effective treatments that can help, and there is no need to struggle alone. Getting help may make it easier to manage your symptoms and to live the kind of life you would like to live.

Best wishes,

Researcher/PWP Providing Support Name"

Similar actions will be taken for email responses as for telephone contacts (see section above). Follow-up emails may be necessary to either further clarify responses to questions, provide further guidance and support, or provide more detailed signposting for help.

14.10 Risk register

All risk alerts whether via email or telephone contact will be logged on a risk register with any action taken, by whom and when (see below). Site researchers will follow up on risk alerts within 1 working day using the risk assessment and reporting SOP including responding to participant and registering the action taken. This will need to be logged at each local site and shared centrally with the lead site (Exeter) in an anonymised format.

14.11 Action to take after responding to immediate risk:

- 1. Document action taken on the risk log and a risk report form (see below).
- 2. Send letter electronically or by post to GP documenting information gathered and action taken.
- 3. Seek / offer supervision around support and debriefing as appropriate.

Figure 3

Risk Report Form

Participant Trial Number

Supervisor:	Signed:	Date://_	
Researcher / assessor / supporting PWP: _	Signo	ed: Date:	//
Date action taken://			
Additional notes / actions taken:			
Date reported://			
Immediate risk:			
Prior attempts:			
Prevention:			
Actions:			
Plans:			
Suicide risk information: [note answers to Intention:	all questions above re	e yes/no answers and (details]

15. DISSEMINATION POLICY

There is an overall dissemination policy for the project, within which there is a specific dissemination policy for the trial results, however aspects of the policy may not be applicable depending on the outcome of this Phase II feasibility trial.

Key aspects of the dissemination policy for the trial include:

- (i) the Consort Guidelines and checklist are reviewed prior to generating any publications for the trial to ensure they meet the standards required for submission to high quality peer reviewed journals etc. http://www.consort-statement.org/
- (ii) Anonymised data arising from the trial is owned by UNEXE as trial lead, lead for trial design, CTU, and trial analysis, and developer of the intervention, managed by UNEXE as the data controller.
- (iii) On completion of the trial, the data will be analysed and tabulated and a Final Trial Report prepared, and made publicly available on the trial website and via the funder. This will be published before the end of the grant.
- (iv) Our publication policy stipulates that all potential publication plans need to be reviewed by the Project Steering Committee before release of data to coordinate activity between partners, determine appropriate authorship and avoid duplication and replication of effort.
- (v) Authorship will be determined on standard criteria (i.e., consistent with the criteria for individually named authors or group authorship such as The International Committee of Medical Journal Editors defined authorship criteria for manuscripts submitted for publication http://www.icmje.org/recommendations/browse/roles-and-responsibilities/defining-the-role-ofauthors-and-contributors.html#two) and will require contributions with respect to design of the study, development of paradigms and interventions within the study, involvement in delivery of the trial, data analysis and/or writing up of the paper. Seniority of authorship will be determined by relative contribution on these elements - individuals leading on design, analysis and write-up of papers will have lead authorship, with this typically following pre-allocated lead roles for the work packages in the grant in the first instance, unless deferred. All papers will include a detailed statement of the relevant author contributions following a standard template.
- (vi) All publications as well as all tools described in this section will acknowledge funding from the UKRI Adolescence, Developing mind and Mental Health scheme.
- (vii) There are plans to notify the participants of the outcome of the trial, through a combination of a specifically designed newsletter, blog, vlog, videos and website, communicated to participants via email and relevant social media on completion of the study.
- (viii) It is possible for the participant to specifically request results from their PI and this information be provided after the results had been published.
- (ix) The trial protocol, full trial report, anonymised participant level dataset, and statistical code for generating the results will be made publicly available.

APPENDIX

Appendix 1: Feasibility Outcomes

Feasibility	Outcomes				
_	people accessed study web site				
Number of	people complete screening				
questions					
Number of	people screened out	If Yes - Reason	Report by demographics		
Number of	people consented		Report by demographics		
Number of	people randomised		Report by demographics		
Blinding rar	ndomisation maintained	Yes	No		
Study arms					
sbLICBT	Number attended group session	Report by demo	graphics		
	Number completed baseline	Data completion of each item for each outcome			
	outcome measure	measure			
	Number completed end of	Data completion	n of each item for each outcome		
	treatment outcome measures	measure			
	Number completed final outcome	Data completion	n of each item for each outcome		
	measures 12-week post baseline	measure			
	Number of participants requesting support	Report by demo	graphics		
	Number of support episodes requested				
	Number of each type of support	Face to Face	e-mail		
	episode requested		C 111611		
DTC	Number completed baseline		'		
	outcome measure				
	Number completed outcome				
	measures at 6 weeks post baseline				
	Number completed final outcome				
	measures 12-week post baseline				
DTC move to sbLICBT	Number attended group session	Report by demo	graphics		
0.02.02.	Number completed baseline	Data completion	n of Number completed		
	outcome measure	each item for ea			
		outcome measu			
	Number completed end of	Data completion	n of Number completed		
	treatment outcome measures	each item for ea	•		
		outcome measu	re outcome measures		
	Number completed final outcome	Data completion	n of Number completed		
	measures 12-week post baseline	each item for ea	ich final outcome		
		outcome measu	re measures 12-week		
			post baseline		
	Number of participants requesting support	Report by demo	graphics		
	Number of support episodes				
	requested				
	Number of each type of support	Face to Face	e-mail		
	episode requested				

Brief Resilience Scale (BRS)

R	despond to each statement below by circling one answer per row.	Strongly Disagree	Disagree	Neutral	Agree	Strongly Agree
BRS 1	I tend to bounce back quickly after hard times.	1	2	3	4	5
BRS 2	I have a hard time making it through stressful events.	5	4	3	2	1
BRS 3	It does not take me long to recover from a stressful event.	1	2	3	4	5
BRS 4	It is hard for me to snap back when something bad happens.	5	4	3	2	1
BRS 5	I usually come through difficult times with little trouble.	1	2	3	4	5
BRS 6	I tend to take a long time to get over setbacks in my life.	5	4	3	2	1

Scoring: Add the value (1-5) of your responses for all six items, creating a range from 6-30. Divide the sum by the total number of questions answered (6) for your final score.

T-4-1		10
ıotaı	score:	/ 6

My score: ____ (average)

BRS Score	Interpretation
1.00 - 2.99	Low resilience
3.00 - 4.30	Normal resilience
4.31 - 5.00	High resilience

PATIENT HEALTH QUESTIONNAIRE-9 (PHQ-9)

Over the last 2 weeks , how often have you been bothered by any of the following problems? (Use "" to indicate your answer)	Not at all	Several days	More than half the days	Nearly every day
1. Little interest or pleasure in doing things	0	1	2	3
2. Feeling down, depressed, or hopeless	0	1	2	3
3. Trouble falling or staying asleep, or sleeping too much	0	1	2	3
4. Feeling tired or having little energy	0	1	2	3
5. Poor appetite or overeating	0	1	2	3
Feeling bad about yourself — or that you are a failure or have let yourself or your family down	0	1	2	3
7. Trouble concentrating on things, such as reading the newspaper or watching television	0	1	2	3
8. Moving or speaking so slowly that other people could have noticed? Or the opposite — being so fidgety or restless that you have been moving around a lot more than usual	0	1	2	3
Thoughts that you would be better off dead or of hurting yourself in some way	0	1	2	3
For office codi	ng 0 +		total Score:	

Over the last 2 weeks , how often have you been bothered by the following problems? (Use "" to indicate your answer)	Not at all	Several days	More than half the days	Nearly every da
1. Feeling nervous, anxious or on edge	0	1	2	3
2. Not being able to stop or control worrying	0	1	2	3
3. Worrying too much about different things	0	1	2	3
4. Trouble relaxing	0	1	2	3
5. Being so restless that it is hard to sit still	0	1	2	3
6. Becoming easily annoyed or irritable	0	1	2	3
7. Feeling afraid as if something awful might happen	0	1	2	3

Work and Social Adjustment Scale (WSAS)		
Ider	tifier Date	
you imp cond	ole's problems sometimes affect their ability to do certain day-to-day tasks in their lives. To rate problems look at each section and determine on the scale provided how much your problem airs your ability to carry out the activity. This assessment is not intended to be a diagnosis. If you are erned about your results in any way, please speak with a qualified health professional.	
	O 1 2 3 4 5 6 7 8 Not at Slightly Definitely Markedly Very severely	
1	Because of my [problem] my ability to work is impaired. '0' means 'not at all impaired' and '8' means very severely impaired to the point I can't work.	
2	Because of my [problem] my home management (cleaning, tidying, shopping, cooking, looking after home or children, paying bills) is impaired.	
3	Because of my [problem] my social leisure activities (with other people e.g. parties, bars, clubs, outings, visits, dating, home entertaining) are impaired.	
4	Because of my [problem], my private leisure activities (done alone, such as reading, gardening, collecting, sewing, walking alone) are impaired.	
5	Because of my [problem], my ability to form and maintain close relationships with others, including those I live with, is impaired.	
	Total WSAS score = 0
